### **14. GCP, ICH and ETHICAL CONSIDERATIONS**

This study will be conducted in compliance with Good Clinical Practices (GCPs), including International Harmonization (ICH) Guidelines, and in a manner consistent with the 1996 version of the Declaration of Helsinki. In addition, all applicable local, state and federal requirements will be adhered to.

This study is to be conducted in accordance with Institutional Review Board regulations. The investigator will obtain appropriate IRB/ethics committee approval prior to initiating the study.

The study will be registered with [clinicaltrials.gov](http://clinicaltrials.gov).

## 15. STANDARD EVALUATION PROCEDURES

**Table 15.1. Proposed Visits and Study Assessments**  
 (visits are by patient, with both eyes tested)

Activity	Pre-operative	Operative	Postoperative		
	Visit 1	Visit 2	Visit 3	Visit 4	Visit 5
			1 Day	1 Month	3 Months
Informed consent	X				
Demographics	X				
General information: medical history	X				
Surgery		X			
Manifest refraction	X			X	X
Uncorrected distance VA (monocular)	X		X	X	X
Corrected distance VA (monocular)	X			X	X
Corneal aberrations	X				X
Ocular aberrations (site specific)	X				X
Subjective questionnaire	X				X
Monitor for adverse events		X	X	X	X
Complete Exit Form 					X

 Complete Exit Form upon termination of subject participation, or at Visit 5, whichever occurs first.

## 16. CONFIDENTIALITY

No protected health information (PHI), including the patient’s name and date of birth, will be collected for study purposes; to ensure this, no PHI is permitted to be entered on any of the Case Report Forms (CRFs). Subjects will only be identified by subject IDs, and identities will be removed at the initial visit so that there is no further need to protect or destroy the information. Collected information will be used for purposes of this study. No information will be sold to third parties, though the de-identified data collected may be used for additional research.

## 17. FINANCIAL AND INSURANCE INFORMATION/STUDY RELATED INJURIES

Every effort to prevent study-related injury will be taken by the Study Doctor and staff. In the event that a patient is injured as a direct result of the study while following the Study Doctor’s instructions and the study requirements, the patient will be instructed to contact his or her doctor immediately. The Study Doctor is to treat the injured subject as needed for those injuries caused directly by this research study. In the event of injury or illness caused by or occurring during a subject’s participation in this research study, all charges for medical care provided to the subject will be billed to his or her insurance company. Neither the Study Doctor nor the Sponsor offer to cover the medical care costs for injuries or illnesses that are not caused directly by the research study. The Sponsor

does not offer to provide any other compensation, unless specifically agreed to elsewhere in this document. This information will be provided to each study subject before the start of the study in the consent form.

## **18. STUDY ENDPOINT CRITERIA**

### ***18.1. Patient Completion of Study***

If a study patient has completed the final visit (Visit 5) of the study, he/she is considered to have completed the study.

### ***18.2. Patient Discontinuation***

Each study patient may voluntarily discontinue the study at any time he/she chooses. Study patients who cannot complete the study for administrative reasons (e.g., non-compliance, failure to meet visit schedule, etc.) will be discontinued from the study. Study patients discontinued during the enrollment phase (prior to surgery) of the study will be replaced.

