#### 9.3.4. Exit Procedures

In the event of premature exit from the study, all study-related examinations should be completed whenever possible. The Exit CRF should be completed, noting that the subject did not complete the study and the reason for premature study exit. If no premature exit from the study occurs, the Exit CRF should be completed at the end of Visit 5 (3 Months Postoperative).

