### **9.6. *Discontinued Subjects***

Discontinued subjects are those who do not have an exit visit or who come into the office to be exited prior to the scheduled final study visit. Subjects may be discontinued from the study at any time if, in the opinion of the investigator, their continued participation in the study poses a risk to their health. The reasons for discontinuation include:

- a. Adverse event;
- b. Lost to follow-up;
- c. Subject decision unrelated to an adverse event;
- d. Protocol violation;
- e. Treatment failure;
- f. Fear of exposure to infectious disease
- g. Other.

To ensure the safety of all subjects who discontinue prior to Visit 5, investigators should assess each subject and, if necessary, advise them of any therapies and/or medical procedures that might be needed to maintain their health. Any changes in medical health and/or use of concomitant medications should also be captured.

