## **10. ANALYSIS PLAN**

### **10.1. *Analysis Data Sets***

All subjects who are enrolled in the study will be evaluated for safety. Efficacy analyses will be performed based on data from those eyes for which uncomplicated LASIK was completed.

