## **11. SAMPLE SIZE JUSTIFICATION**

The sample size has been chosen to be similar to that for comparable Contoura, WFO, WFG and ray tracing LASIK studies published in the peer-reviewed literature. Each of four sites will enroll up to 50 eyes, for a total potential study population of 140 eyes. With an expected 10% dropout rate before the 3M visit, 126 eyes would be available for analysis.

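### Section 18.2's administrative discontinuation rule has no exception after surgery, so a site could exit a treated subject who can still give a 3-month refraction

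*Combined protocol and SAP*

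**What the plan says.** Section 18.2 sets the rule: "Study patients who cannot complete the study for administrative reasons (e.g., non-compliance, failure to meet visit schedule, etc.) will be discontinued from the study". Its next sentence reads "Study patients discontinued during the enrollment phase (prior to surgery) of the study will be replaced". Surgery therefore matters in that section only for replacement. Discontinuation after surgery is foreseen, is not exempted, and carries no provision for replacement.

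Section 18.1 defines completion by Visit 5 alone. Section 9.6 counts as discontinued those without an exit visit and those "who come into the office to be exited prior to the scheduled final study visit". For these subjects it adds: "To ensure the safety of all subjects who discontinue prior to Visit 5, investigators should assess each subject". Section 9.3.4 says: "In the event of premature exit from the study, all study-related examinations should be completed whenever possible".

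On the analysis side, section 10.1 states: "Efficacy analyses will be performed based on data from those eyes for which uncomplicated LASIK was completed". Sections 10.2 and 10.3 give no rule for missing, early or out-of-window values. Section 11 states: "With an expected 10% dropout rate before the 3M visit, 126 eyes would be available for analysis".

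**The concern.** Once both eyes have been operated on, the only study requirement left to the subject is to attend and be measured. Exit at that point does not change exposure to the treatment; it only stops outcome collection. The two examples in section 18.2, non-compliance and failure to keep to the visit schedule, describe conduct that does not in itself prevent a refraction at 3 months. The wording is nevertheless mandatory.

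The primary outcome is residual refractive cylinder, and the hypothesis in section 3 concerns the share of eyes at 0.25 D or less in a 3-month evaluation. Each subject exited early can cost two eyes. Subjects who miss visits may differ in outcome from those who attend, being either very content or very unhappy. The study has one arm and is to be set against published results, so no concurrent control would show the effect of selective loss.

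**Working it through.** **1. The plan's own figure.** Sections 7.1 and 11 give 140 eyes of 70 subjects and 10% dropout. 140 × (1 − 0.10) = 126 eyes, which reproduces section 11. The allowance is 140 − 126 = 14 eyes, or 7 subjects. Section 11 does not split the 10% by cause, so the administrative share is unknown.

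**2. What happens to a treated subject who falls off schedule.** Table 9.3-1 gives Visit 3 at 1 to 7 days, Visit 4 at 1 to 2½ months and Visit 5 at 2½ to 5 months.

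- Exited after missing Visit 3: an exit examination held promptly falls well before 2½ months and is not a 3-month result.
- Exited after the Visit 4 window closes: an exit examination falls at 2½ months or later and can lie inside the Visit 5 window.
- Exited without coming in: there is no exit refraction. Section 9.6 foresees this case.
- Seen after 5 months: a refraction exists, but no rule says whether it is used.

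In none of these cases does the protocol ask the subject to come back at 3 months. Section 9.6 asks for a safety assessment and section 9.3.4 for examinations at exit. Section 10.1 keeps the eye in the efficacy set, but membership of the set does not supply a value.

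**3. Bounds on the reported rate.** The protocol gives no expected success rate, so a range is assumed. Let p be the rate among observed eyes and m the number of missing eyes. The rate over all 140 treated eyes lies between p(140 − m)/140 and [p(140 − m) + m]/140, a width of m/140.

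| Assumed p | m = 14: lower | m = 14: upper |
|---|---|---|
| 70% | 63.0% | 73.0% |
| 80% | 72.0% | 82.0% |
| 90% | 81.0% | 91.0% |

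The width is 14/140 = 10 points in each row. If only 4 of the missing eyes were administrative, their part would be 4/140 = 2.9 points.

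**4. Illustrative bias.** If the missing 10% succeed d points less often than the observed eyes, the all-treated rate is 0.9p + 0.1(p − d) = p − 0.1d, and the reported rate is too high by 0.1d. For d = 10, 20 and 30 this is 1, 2 and 3 points. If the missing eyes do better, the sign reverses.

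**5. Precision.** Half-width = 1.96 × √[p(1 − p)D/n], with p = 80% assumed. D = 1 treats eyes as independent. D = 1.5 corresponds to an assumed between-eye correlation of 0.5.

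| n | D = 1 | D = 1.5 |
|---|---|---|
| 126 | 7.0 points | 8.6 points |
| 140 | 6.6 points | 8.1 points |

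Recovering all 14 eyes gains about half a point at most. Selective loss is the larger issue.

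**The case against.** The strongest reply is that section 18.2 applies only to a subject who cannot complete the study, and section 18.1 defines completion as Visit 5. Read together, a subject who missed an interim visit but can attend Visit 5 does not meet the condition. A reader might infer that the protocol orders exit after any single missed visit. The text does not say so; that is one possible reading. What remains is that the examples point to conduct that does not prevent Visit 5, so the condition and its examples pull apart and a site could act on either.

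A reader might also take the protocol-violation entry in section 9.6 as a second trigger. It stands in a list of reasons, after a sentence that permits discontinuation where continued participation poses a health risk. It is better read as a category to record, so limiting it would retain nobody.

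Nor can it be said that the data are simply given up. Exit examinations can include the refraction, section 10.1 excludes no eye for discontinuation or non-compliance, and the windows are wide and adjoin. Section 18.5 ties the end of the study to Visit 5 or termination, and section 9.1 pays the $500 rebate on completing the 3-month visit. These points reduce the likely loss. They do not require a treated subject who has been exited to return, and such a subject may lose the rebate as an incentive.

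Finally, a reader might add administrative exits on top of the 10% dropout. Section 11 does not limit that figure by cause, so a further loss would be assumed and might be counted twice.

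**Conclusion.** The point holds as a gap in wording with a possible effect on the primary result. The administrative rule is mandatory, has no exception after an irreversible one-time treatment, and can be read as telling a site to exit subjects who could still be measured. Nothing elsewhere brings them back at 3 months.

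The size cannot be derived from the protocol. If administrative exits sit within the 10% dropout, the ceiling is 14 of 140 eyes, with worst-case bounds 10 points wide; the administrative part is unknown and could be small. The 1 to 3 point inflation assumes that all 14 eyes are missing and that they succeed 10 to 30 points less often. The protocol supports neither that gap nor its direction. This is a cheap improvement to make before enrolment; it does not show that the design fails.

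**What to change.** In section 18.2, limit administrative discontinuation to subjects not yet operated on. Then add wording to this effect:

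- After surgery, a missed or out-of-window visit, other non-compliance or a protocol deviation does not end follow-up.
- The subject is still invited to Visit 5.
- The refraction obtained is kept with its actual day after surgery and flagged if out of window.

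In section 10, state that where a treated eye lacks Visit 5, a sensitivity result will be reported using its Visit 4 or exit refraction. Visit 4 refraction is already scheduled.

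Leave the list of reasons in section 9.6 unchanged, and leave the right to withdraw voluntarily untouched. Section 18.3, on termination for severe adverse events, is a separate rule and is not addressed here.

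The cost is a few sentences, with no added visits or subjects. The downside is some off-schedule Visit 5 data that need a flag.

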### ***18.3. Patient Termination***

A study patient will be terminated if the study patient develops any severe adverse event that may be related to the study. A study patient will receive appropriate treatment at the discretion of the investigator. Notification of termination will be clearly documented. These study patients are considered to have completed the study and will not be replaced.

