### ***18.5. Study Completion***

The study will be complete when all enrolled patients have completed Visit 5 or have been terminated from the study.

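### Section 18.3 ends observation after a severe, possibly related adverse event and labels the subject a completer, so 3-month safety and refraction data may be lost because of a safety event

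*Combined protocol and SAP*

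**What the plan says.** All references are to the combined protocol and SAP.

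- **Section 18.3** sets a mandatory rule: "A study patient will be terminated if the study patient develops any severe adverse event that may be related to the study". On status it adds: "These study patients are considered to have completed the study and will not be replaced".
- **Section 9.6** counts as discontinued those without an exit visit and those "who come into the office to be exited prior to the scheduled final study visit". Adverse event is the first listed reason. Its closing paragraph asks investigators to assess everyone who leaves before Visit 5 and to capture changes in health and medication.
- **Section 9.3.4** covers premature exit: "The Exit CRF should be completed, noting that the subject did not complete the study and the reason for premature study exit". It also asks that "all study-related examinations should be completed whenever possible".
- **Section 18.1** says: "If a study patient has completed the final visit (Visit 5) of the study, he/she is considered to have completed the study". **Section 18.5** says: "The study will be complete when all enrolled patients have completed Visit 5 or have been terminated from the study".
- **Section 8** names residual refractive cylinder as the primary outcome. Its safety measures are change in corrected distance visual acuity (CDVA) and the satisfaction, vision quality and symptom questionnaire.
- **Tables 9.3-2 and 15.1** schedule postoperative refraction and CDVA at Visits 4 and 5 only, and the postoperative questionnaire at Visit 5 only. **Table 9.3-1** opens the Visit 5 window at 2½ months.

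**The concern.** There are two linked problems.

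First, one subject receives two opposite labels. Someone exited at six weeks for a severe, possibly related event is a completer under Section 18.3, but discontinued under Section 9.6 and a non-completer on the Exit CRF under Section 9.3.4. A site cannot record both. The exit examinations and the early-leaver assessment are written for premature exits and discontinuations, so a site that takes the completer label literally could doubt that they apply.

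Second, the rule ends observation in a group selected by a safety event. In a study with continuing treatment, a stopping rule of this kind protects the subject by withdrawing the treatment. Here both eyes are treated at Visit 2, and afterwards there is nothing to withdraw. The rule can only remove later data: 3-month CDVA, the questionnaire, and the refraction behind the primary outcome. Missing values that arise because of a safety event are the kind a safety summary can least afford, even when they are few.

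**Working it through.** **1. The labels side by side.** Take a subject with completed bilateral surgery and a severe, possibly related event before Visit 5.

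| Section | Status |
|---|---|
| 18.3 | Terminated; deemed to have completed |
| 9.6 | Discontinued, reason adverse event |
| 9.3.4 | Exit CRF records non-completion and the reason |
| 18.5 | Termination listed as an alternative to completing Visit 5 |

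Section 18.3 conflicts with 9.6 and 9.3.4 on the label. It fits awkwardly with 18.5.

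**2. What is at risk, by time of termination** (from Tables 9.3-1, 9.3-2 and 15.1).

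| Termination | Scheduled data in hand | At risk |
|---|---|---|
| After surgery, before Visit 4 | No postoperative refraction, CDVA or questionnaire | All three at 3 months |
| After Visit 4, before 2½ months | 1-month refraction and CDVA | 3-month refraction and CDVA; any postoperative questionnaire |
| From 2½ months, before Visit 5 is done | As above | Nothing, if the exit examination is done, since it falls in the window |
| At or after Visit 5 | All | Nothing |

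The exposed group is therefore subjects terminated after surgery and before 2½ months. Aborted or unsuccessful operations have their own exit rules in Sections 7.4 and 9.3.2 and are not counted here.

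**3. What the plan does to limit the loss.**
- Section 9.3.4 requests exit examinations, which can include CDVA and the questionnaire. This is best effort, and before 2½ months it does not give a 3-month value.
- The Section 9.6 assessment names neither CDVA nor the questionnaire.
- Section 9.5 allows unscheduled examinations at the investigator's discretion.
- Section 13.3 records the outcome of the event, and Section 13.5 tabulates ocular events. Neither gives 3-month acuity or symptom status.
- Section 13.4 maintains care and requires follow-up data to be documented and available, but the coordinator and Medical Monitor decide when they go on the CRFs.

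No section sends a terminated subject to Visit 5.

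**4. Size.** Inputs: 140 eyes of 70 subjects (Section 7.1) and 10% dropout before the 3-month visit (Section 11).

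The plan's own figure: 140 × (1 − 0.10) = 126 eyes, which reproduces. If dropout is by subject, that is 70 × 0.10 = 7 subjects lost and 63 remaining.

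Let k be the number of subjects terminated before the window with no 3-month value. The documents give no rate of severe related events, so k is an assumption, shown for 1 to 3. Eyes lost are at most 2k/140. Section 11 gives one overall dropout rate, so the k subjects are taken to be among the 7. Following them to Visit 5 would leave (7 − k)/70 subjects without a 3-month CDVA.

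| k | Eyes lost, at most | Subjects missing, as planned | Subjects missing, if the k are followed |
|---|---|---|---|
| 1 | 2/140 = 1.4% | 7/70 = 10.0% | 6/70 = 8.6% |
| 2 | 4/140 = 2.9% | 7/70 = 10.0% | 5/70 = 7.1% |
| 3 | 6/140 = 4.3% | 7/70 = 10.0% | 4/70 = 5.7% |

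**The case against.** The best defence is that little depends on this. The completer label changes no analysis set: Section 10.1 evaluates all enrolled subjects for safety and bases efficacy on eyes with uncomplicated surgery. Section 18.2 has just dealt with replacing subjects lost before surgery, so the word in 18.3 may serve only enrolment accounting. The severe event is still recorded, and if ocular it is tabulated. CDVA is also scheduled at 1 month, and Section 8 does not tie that safety measure to 3 months. The number affected is probably small, and follow-up stays voluntary, so no amendment can guarantee a value.

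Most of this stands, and it limits the weight of the point. It does not remove it. The two labels still cannot both be recorded, and the plan itself orders observation to stop when a visit already scheduled for every subject would supply the data.

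A reader might infer more than the documents support:

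- *That 18.3 contradicts 9.6 on whether exit is mandatory.* Section 9.6 says "Subjects may be discontinued from the study at any time if, in the opinion of the investigator" judges continued participation a health risk. That is a general discretion. Section 18.3 is a specific rule for one class of event, and both can be obeyed.
- *That 18.1 flatly contradicts 18.3.* Section 18.1 can be read as a sufficient condition for completion, not the only one.
- *That these losses come on top of the 10%.* Section 11 states a single dropout rate before the 3-month visit and sets no terminations apart.
- *That the rule makes safety look better than it is.* Section 13.3.1 defines severe as incapacitating, which need not involve vision. The 3-month status of these subjects is unknown, and so is the direction of bias.

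**Conclusion.** The point holds as a limited one that should be corrected. Section 18.3 labels as completed an exit that Sections 9.6 and 9.3.4 record as a discontinuation and non-completion. After surgery, its only practical effect on the study is to end observation. For terminations before 2½ months, the 3-month CDVA, the only scheduled postoperative questionnaire and the 3-month refraction may be missing because of a safety event. The existing safeguards reduce this but do not ensure a 3-month value.

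The size is at most 2 of 140 eyes (1.4%) per subject. This assumes that both eyes are lost and no usable in-window examination is obtained. The total cannot be derived without an event rate; it is probably small and lies within the stated dropout. The concern is why the data go missing, more than how many.

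**What to change.** Amend Section 18.3 so that a severe, possibly related event after surgery does not end data collection:

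1. With the subject's continued consent, and whatever clinical care the investigator chooses, follow to the scheduled Visit 5 for refraction, CDVA, questionnaire and adverse event outcome.
2. Remove the completer label. Class any such subject who still exits early as discontinued for an adverse event, in line with Sections 9.6 and 9.3.4.
3. List every treated eye without a 3-month CDVA, with its last value and the reason.

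The cost is minor rewording and one listing; no visit is added. Reported safety or efficacy figures may shift slightly, possibly in the less favourable direction, once these subjects contribute 3-month data.

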### ***18.4. Study Termination***

The investigator with appropriate notification may terminate the study. If, after clinical observations, the investigator feels that it may be unwise to continue the study, he may stop the study.

